6.5.1.1. Demographic Summary

The following demographic will be summarized by number and percentage:

- Gender (male, female).
- Age (<65, ≥65).
- Race (White, Black or African American, Asian, American Indian or Alaska Native, Native Hawaiian or other Pacific Islander, Other, Not Reported).
- Ethnicity (Hispanic/Latino, not-Hispanic/Latino).

Age (continuous) will be summarized with descriptive statistics (mean, median, standard deviation, minimum, and maximum).

6.5.1.2. Baseline and Disease Characteristics

The following baseline and disease characteristics will be summarized:

- Location of primary tumor.
- Stage at initial diagnosis.
- Stage at study entry.
- Tumor histology.
- Time since initial diagnosis, defined as [date of first dose – date of initial diagnosis]/30.4375.
- Baseline tumor burden in the brain (1 to 2 brain lesions vs. ≥3 brain lesions).
- Lactate dehydrogenase (LDH) level at baseline.
- ECOG performance status.
- Local and central laboratory assessments of *BRAF* status. Local assessment results will be based on the data collected on the “Local BRAF Results” eCRF page.

6.5.1.3. Medical History

Medical history reported at the time of the Screening will be coded using the latest Medical Dictionary for Regulatory Activities (MedDRA) terminology available at the time of reporting. Medical history will be summarized by primary system organ class (SOC) and preferred term (PT). Each patient will be counted only once within each PT or SOC.

6.5.1.4. Prior Anticancer Treatments

Prior anticancer treatments include systemic therapy, radiation and surgery.

The number and percentage of patients who received, separately, any prior anticancer systemic treatment, radiotherapy, or surgery will be summarized.

Prior anticancer systemic treatment will be summarized as follows:

- Total number of regimens (there can be more than one medication per regimen),
- Number of regimens for checkpoint inhibitor. The final list of checkpoint inhibitors will be provided upon medical review of all prior anticancer therapies.
- Setting at last medication.
- Best response at last medication (defined as the best response during the last treatment regimen recorded).
- Reason for discontinuation at last medication.
- Time (in months) from end of last medication to study start date.
- Time (in months) from start of last medication to disease progression. The last medication is defined based on the last end date of all prior regimen components.

Prior anticancer systemic treatment will also be summarized by Anatomical Therapeutic Chemical (ATC) class and preferred term.

For prior anticancer radiotherapy, information about the last radiotherapy (based on end date) will be summarized: time (in months) between radiotherapy and start of study treatment, location and best response. In addition, prior local brain radiotherapy will be summarized (location = “Brain” in the Prior Cancer Treatment Radiation CRF page).

For prior anticancer surgery, the time (months) between last surgery and start of study treatment, site, location, whether the surgery was palliative, and the result will be summarized. In addition, prior local brain surgery will be summarized (location = “Brain” in the Prior Cancer Treatment Surgery CRF page).

All prior anticancer therapies will be presented in a data listing separately for systemic treatment, radiotherapy, and surgery.

Incomplete dates will be handled as described in [Section 5.3.1](#).

6.5.2. Study Conduct and Patient Disposition

6.5.2.1. Patient Disposition

The disposition summary will be created for the Safety Lead-in and the Phase 2 portion of the study separately.

The following disposition categories will be summarized:

- Number (%) of patients who received at least one dose of study drug.

- Number (%) of patients who are still on treatment.
- Number (%) of patients who discontinued the treatment:
 - Primary reasons for treatment discontinuation.
- Number (%) of patients who discontinued the treatment but are still in long-term follow-up.
- Number (%) of patients who discontinued the study:
 - Primary reasons for study discontinuation.

The number and percent of participants enrolled by region, country and site, and the number and percent of participants in each analysis set as described in [Section 4](#) will also be summarized.

Screen failure patients are those who were screened, but never started the study treatment for any reason. The data collected on these patients will not be included in any analyses.

COVID-19 Related Disposition

A listing of all patients affected by COVID-19 related study disruption will be created. The listing will present subject number identifier by investigational site, and a description of COVID-19 related events including:

- Protocol deviations.
- Adverse events treatment.
- Treatment discontinuation.
- Study discontinuation.
- Death.

6.5.2.2. Protocol Deviations

Potentially important protocol deviations (PIPDs) will be compiled prior to database closure and will be summarized by category and also presented in a listing. Categories will be assigned by the study Clinician.

In addition, PIPDs related to COVID-19 will be presented in a separate listing.

6.5.3. Study Treatment Exposure

Duration of Exposure

- **Intended treatment duration** (days) = end of treatment date – date of first dose of study drug +1.
 - If a patient permanently discontinues both binimetinib and encorafenib, end of treatment date is the date of last dose of the study drug;
 - If a patient permanently discontinues binimetinib but is still on single-agent encorafenib treatment, end of treatment date is the date of last dose of encorafenib treatment.
- **Actual treatment duration** (days) = date of last non-zero dose of the study drug - date of first dose of study drug +1

Cumulative Dose

Cumulative dose is defined as:

- **Intended cumulative dose** (mg) = sum of all protocol specified doses across intended treatment duration.
- **Actual cumulative dose** (mg) = sum of all actual doses that the patient received across actual treatment duration.

For patients who did not take any drug the actual cumulative dose is by definition equal to zero.

Dose Intensity

- **Intended dose intensity** (mg/day) = intended cumulative dose / intended treatment duration.
- **Actual dose intensity** (mg/day) = actual cumulative dose / intended treatment duration.
- **Relative dose intensity** (%) = $100 * (\text{actual dose intensity} / \text{intended dose intensity})$.

A summary of exposure, including duration of exposure, cumulative dose, actual dose intensity, and relative dose intensity (including categories <50%, 50%-<75%, 75%-<90%, 90%-<110%, and $\geq 110\%$, if applicable), will be presented for each study drug.

Actual treatment duration will be summarized in months including descriptive statistics (n, mean, median, minimum, maximum) and will also be categorized by time intervals (eg, <1 months, 1-3 months, etc. as appropriate for the protocol) for which frequency counts and percentages of patients will be provided.

Actual treatment duration, cumulative dose, actual dose intensity, and relative dose intensity will also be listed for each patient by treatment arm.

6.5.3.1. Dose Modification

Dose modification will be summarized based on the the dosing data collected on the study treatment CRF page.

Dose Reduction

Dose reductions are permitted for encorafenib and binimetinib and will be summarized based on the dose modification data collected on the respective study medication eCRF page.

The number and percentage of patients with at least one dose reduction as well as a breakdown of dose reductions (1/2/ \geq 3) will be summarized.

Reasons for dose reductions will also be summarized. Patients can contribute to more than one reason if multiple dose reductions occurred for different reasons, but will only be counted once per reason. Percentages will be calculated based on the total number of patients in the safety analysis set.

Dose Interruption

A dose interruption will be indicated in the study medication eCRF. For encorafenib (Safety Lead-in) and binimetinib, a total dose of 0 mg in the morning and/or in the evening indicates a dose interruption. If a patient had a total dose of 0 mg both in the morning and in the evening, it is counted as one dose interruption for this patient. For encorafenib (Phase 2), a dosing record with a total daily dose of 0 mg for one or more days indicates a dose interruption. If the start and stop date of two dose interruption records are consecutive, it will be counted as one dose interruption.

Dose interruption will be summarized based on the dose modification data collected on the eCRF page. However, in order not to over count interruptions, dosing records with 0 mg entered as last dosing record will not be counted as interruptions. Those represent the reason for permanent discontinuation and will therefore be presented in the reason for treatment discontinuation analysis.

The number and percentage of patients with dose interruptions and the corresponding reasons will be summarized. Patients can contribute to more than one reason if multiple dose interruptions occurred for different reasons, but will only be counted once per reason. Percentages will be calculated based on the total number of patients in the safety analysis set.

6.5.4. Concomitant Medications

Concomitant medications are medications, other than study medications, which started prior to first dose of study treatment and continued during the on-treatment period (see [Section 5.2.5](#)) as well as those started during the on-treatment period. Concomitant

medications will be coded in the WHO Drug coding dictionary and will be tabulated by ATC classification level 2 and PT (level 4) by decreasing frequency. In case of equal frequency regarding drug class (respectively drug name), alphabetical order will be used. A patient will be counted only once within a given drug name, even if he/she received the same medication at different times.

All concomitant medications will be presented in a data listing.

Incomplete dates will be handled as described in [Section 5.3.1](#).

6.5.5. Subsequent Anticancer Therapies/Procedures

Number of patients with any anticancer treatment after discontinuation of study treatment will be summarized by type of therapy (systemic treatment, radiotherapy, and surgery).

Summary statistics will be created for the data collected on the “Subsequent Cancer Treatment Systemic” eCRF page.

Subsequent anticancer systemic treatment will be summarized by ATC class and preferred term and will also be presented in a listing.

Incomplete dates will be handled as described in [Section 5.3.1](#).

6.6. Safety Summaries and Analyses

Safety data will be presented in tabular and/or graphical format and summarized descriptively, where appropriate.

6.6.1. Adverse Events

All analyses will be based on TEAEs as defined in [Section 3.4.1](#) unless otherwise specified. AEs not considered treatment emergent will be flagged in data listings.

Seriousness, toxicity grade, action taken (interruption, reduction, and withdraw) of AEs are as reported by the Investigator on the “Adverse Events” CRF.

A high level summary of AEs will include the number and percent of patients with:

- Any TEAEs.
- Serious TEAEs.
- TEAEs with CTCAE Grade ≥ 3 .
- Related TEAEs to:
 - Encorafenib;

- Binimetinib;
- Both encorafenib and binimetinib.
- Related serious TEAEs:
 - Encorafenib;
 - Binimetinib;
 - Both encorafenib and binimetinib.
- TEAEs leading to dose interruption of:
 - Encorafenib;
 - Binimetinib;
 - Both encorafenib and binimetinib.
- TEAEs leading to dose reduction of:
 - Encorafenib;
 - Binimetinib;
 - Both encorafenib and binimetinib.
- TEAEs leading to permanent discontinuation from:
 - Encorafenib;
 - Binimetinib;
 - Both encorafenib and binimetinib.
- TEAEs leading to dose reduction of any study drug due to COVID-19.
- TEAEs leading to permanent discontinuation from any study drug due to COVID-19.

Each unique AE at the PT level in each treatment arm of the study for a patient is included in the count.

Adverse Events by SOC and PT

The following summaries will be created by SOC and PT by decreasing frequency:

- TEAEs by maximum toxicity grade (all causality).
- TEAEs by maximum toxicity grade (treatment related).
- COVID-19 related TEAEs (all causality).
- Serious TEAEs by maximum toxicity grade (all causality).
- Serious TEAEs by maximum toxicity grade (treatment related).
- TEAEs leading to dose reduction of any study drug due to COVID-19.
- TEAEs leading to permanent discontinuation from any study drug due to COVID-19.

An event will be considered treatment related if the Investigator considered the event related to the study drug or this information is unknown.

Adverse Events by PT Only

The following summaries will be created by AE PT by decreasing frequency:

- TEAEs (all causality) experienced by $\geq 10\%$ of patients in Safety Lead-in and in at least one cohort for Phase 2.
- Treatment related TEAEs experienced by $\geq 10\%$ of patients in at least one cohort (Phase 2).
- TEAEs with CTCAE Grade ≥ 3 (all causality) by PT and maximum toxicity grade.
- Serious TEAEs (all causality).
- COVID-19 related serious TEAEs (all causality).

Adverse Events Leading to Dose Modification by PT

The following summaries will be created by PT by decreasing frequency:

- TEAEs leading to dose interruptions by maximum toxicity grade (all causality).
- TEAEs leading to dose reductions by maximum toxicity grade (all causality).
- TEAEs leading to permanent discontinuation by maximum toxicity grade (all causality).

The AE by PT summary will be created separately for:

- Encorafenib;

- Binimetinib.

Each patient will be counted only once within each PT.

Adverse Events in Patients with Dose Escalation in Phase 2

TEAEs leading to dose interruptions, dose reductions and permanent discontinuation will also be summarized by PT for patients who escalate to encorafenib 600 mg QD in Phase 2.

All AEs and their attributes will be presented in data listings sorted by patient identifier, AE and date of onset of the AE.

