4.2. Discussion of Study Design

This Phase 2 trial uses accepted tumor assessment endpoints with a primary endpoint of response, BMRR. Predefined, standardized and generally accepted criteria for this patient population are used to ascertain responses, specifically RECIST v1.1 and mRECIST v1.1. Response rate is deemed a direct measure of drug antitumor activity that can be evaluated in a single-arm trial ([US Department of Health and Human Services 2007](#)).

The study design incorporates a Safety Lead-in to ensure an appropriate safety evaluation of a previously untested dosing regimen. If the high-dose regimen is determined to be safe based on the Safety Lead-in results, the stratified randomized study design provides an unbiased approach to evaluate the efficacy and safety of 2 dosing regimens. If the high-dose regimen is determined not to be safe based on the Safety Lead-in results, the 2 cohorts in the standard-dose treatment arm will allow the evaluation of the efficacy of standard-dose regimen in those patients with prior local therapy and those without prior local therapy in order to better understand the impact, if any, of prior local therapy on objective response to subsequent systemic therapy with encorafenib and binimetinib.

Patients who are able to tolerate the standard dose of encorafenib (450 mg QD) plus binimetinib (45 mg BID) during the first 4 weeks of treatment (Cycle 1) should be dose-escalated to 600 mg encorafenib QD plus 45 mg binimetinib BID provided they meet protocol-defined criteria (see [Section 6.7.2](#)). This update in protocol amendment version 3.0 provides additional data to evaluate the safety, tolerability and efficacy of encorafenib + binimetinib combination therapy with dose-escalation to encorafenib 600 mg QD.

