6.7.2. Intra-Patient Dose Escalation of Encorafenib

During the Phase 2 part of the study, all patients will begin treatment with standard doses of encorafenib (450 mg QD) plus binimetinib (45 mg BID). Patients who are able to tolerate the standard dose of encorafenib (450 mg QD) plus binimetinib (45 mg BID) during the first 4 weeks of treatment (Cycle 1) should be dose-escalated to 600 mg encorafenib QD plus 45 mg binimetinib BID provided the following criteria are met:

- Must not have experienced a clinically meaningful treatment-related adverse event of CTCAE \geq Grade 2 that based on investigator assessment prohibits escalation.
- Requires no dose reductions during the first 4 weeks (Cycle 1; guidelines for dose reductions are detailed in [Appendix 2](#) for encorafenib and [Appendix 3](#) for binimetinib). However, a single dose interruption of up to 4 days is permitted during Cycle 1. To ensure steady state exposures of encorafenib + binimetinib in patients undergoing intra-patient dose escalation, 7 days of consecutive dosing at the starting doses (450 mg QD encorafenib + 45 mg BID binimetinib) are required prior to the intra-patient escalation (600 mg QD encorafenib + 45 mg BID binimetinib).

Therefore, intra-patient dose escalation should occur on Cycle 2 Day 1 (+ 7 days).

Investigators must confirm patients meet all criteria to qualify for dose escalation. Patients who cannot tolerate 600 mg QD encorafenib plus 45 mg BID binimetinib will be dose reduced to 450 mg QD encorafenib plus 45 mg BID binimetinib. Re-escalation up to 600 mg QD will not be permitted. Additional dose delays or reductions will be permitted for toxicity management as outlined in [Table 8](#).

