3.4.1. Adverse Events

An AE is considered a treatment-emergent adverse event (TEAE) if the event starts on or after the first dosing day and time/start time, if collected, but before the last dose +30 days, or start of subsequent anticancer *drug* therapy minus 1 day, whichever occurs first. Any events that started prior to date of the first dose are not considered TEAEs. If an AE starts on the same day as date of the first dose, it will be considered treatment emergent unless the CRF data indicates otherwise via explicitly recording time for AE onset and treatment dosing.

Adverse events will be coded using current Medical Dictionary for Regulatory Activities (MedDRA). Severity of AEs will be graded using the NCI-CTCAE v 4.03 toxicity grading scale.

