5.2. General Methods

Unless otherwise specified, all analyses will be performed separately for the Safety Lead-in and for the Phase 2 portion of the study.

Qualitative/categorical data will be summarized by frequency counts and percentages. Percentages will be calculated using the number of patients in the relevant treatment arm or subgroup as the denominator. Continuous data will be summarized using appropriate descriptive statistics (eg, mean, standard deviation, median, minimum, and maximum) by treatment arm.

For reporting conventions, minimum and maximum values will be presented with the same decimal precision as collected in the raw data; mean, median, and quartiles should generally be presented to one more decimal place than the raw data; standard deviation should be displayed to two more decimal places than the raw data. Percentages will be reported to one decimal place. Unless otherwise noted, for all percentages, the number of patients in the analysis set for the treatment arm who have an observation will be the denominator.

Table summaries will be presented as follows. For Phase 2 portion of the study, patients in a cohort escalating to 600 mg encorafenib QD may also be summarized separately.

For Phase 2, the following analyses will be performed by cohort and overall (Cohort 1 + Cohort 2):

- Demographics and other baseline disease characteristics summary.
- Patient disposition.
- Protocol deviations.

- Efficacy analysis.
- Safety analysis.

The following analyses will be performed by cohort only:

- Study treatment exposure.
- Concomitant medication.
- Subsequent anticancer therapies/procedures.

Data listings will be sorted by cohort, patient identifier, parameter and the corresponding date of assessment. The listing source will be included in the footer of the listings.

Statistical analyses detailed in this SAP will be conducted using SAS[®], version 9.4 or higher (SAS Institute, Inc.). Noncompartmental PK analyses will be performed with Phoenix[®] WinNonlin[®] version 6.4 or higher (Certara USA, Inc., Princeton, NJ).

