5.2.5. On-treatment Period

On-treatment period is defined as the time from the first dose date of any study drug through (minimum of last dose of study treatment +30 days, start day of subsequent anticancer therapy - 1 day).

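### The committed adverse event table for patients escalated to 600 mg counts events from the first 450 mg dose to 30 days after the last dose of any study drug, so it mixes 450 mg and 600 mg events.

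*SAP*

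**What the plan says.** - **The table.** SAP 6.6.1, under the heading on patients with dose escalation: "TEAEs leading to dose interruptions, dose reductions and permanent discontinuation will also be summarized by PT for patients who escalate to encorafenib 600 mg" QD. This is a commitment, and it states no start or end date tied to escalation.
- **The default window.** SAP 6.6.1 opens with "All analyses will be based on TEAEs as defined in" Section 3.4.1, unless otherwise specified. SAP 3.4.1 reads: "An AE is considered a treatment-emergent adverse event (TEAE) if the event starts on or after the first dosing day". The window closes at last dose plus 30 days, or the day before subsequent anticancer drug therapy if earlier. SAP 3.3 defines the last dose as the latest non-zero dose of any study drug. SAP 5.2.5 starts the on-treatment period in the same way: "On-treatment period is defined as the time from the first dose date of any study drug through" its end date.
- **Who escalates.** Protocol 6.7.2 starts Phase 2 patients at 450 mg and escalates at Cycle 2 Day 1, or up to 7 days later. One criterion is "Requires no dose reductions during the first 4 weeks". One interruption of no more than 4 days is allowed. There must be no related Grade 2 or higher event that the investigator judges to prohibit escalation. Patients who cannot tolerate 600 mg return to 450 mg and may not go up again.
- **Other summaries of this group.** SAP 5.2 says that "patients in a cohort escalating to 600 mg encorafenib QD may also be summarized separately". No dating rule is given.
- **Purpose.** Protocol 4.2 says the change "provides additional data to evaluate the safety, tolerability and efficacy of encorafenib + binimetinib combination therapy with dose-escalation to encorafenib 600 mg QD".

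**The concern.** A table meant to inform tolerability with escalation to 600 mg should let the reader see what happened at 600 mg. This one cannot, because its window is too wide at both ends.

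At the start, it takes in 28 to 35 days at 450 mg, a period the patient had to tolerate in order to qualify. At the end, a patient who took 600 mg briefly and then spent months at 450 mg or lower still contributes later interruptions, reductions and discontinuations.

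SAP 6.6.1 also counts each patient once per preferred term in the dose-modification tables. If that rule carries over, a Cycle 1 interruption for a given term hides a second interruption for the same term at 600 mg.

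Protocol 2.2.5 reports that an earlier study stopped treating patients at 600 mg after early-onset Grade 3 creatinine increases in 3 melanoma patients. Readers will therefore look to this table for tolerability at that dose.

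**Working it through.** **1. The plan's own figure.** SAP 5.1.2.2 rejects a response rate of 30% or less if at least 21 of 50 patients respond, with one-sided alpha 5% and about 90% power at 50%.
- Exact binomial: P(X ≥ 21 | n = 50, p = 0.30) = 0.0478, and P(X ≥ 21 | n = 50, p = 0.50) = 0.899.
- A cutoff of 20 gives alpha 0.0848, so 21 is the smallest valid cutoff. The figures reproduce.
- The test counts all patients in a cohort and does not use escalation status, so this point does not touch it.

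**2. Effect of the early start on the committed table.** The documents give no 600 mg rates, so the rates below are assumptions. Let q be the proportion of escalated patients with a qualifying event in Cycle 1 and r the proportion with one at 600 mg, taken as independent. The table shows 1 − (1 − q)(1 − r); the quantity of interest is r.

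| Category | q | r | Shown |
|---|---|---|---|
| Reduction, permanent discontinuation | 0 (by the criteria) | any | r |
| Interruption | 5% | 20% | 1 − 0.95 × 0.80 = 24% |
| Interruption | 30% | 20% | 1 − 0.70 × 0.80 = 44% |
| Interruption | 5% | 40% | 1 − 0.95 × 0.60 = 43% |
| Interruption | 30% | 40% | 1 − 0.70 × 0.60 = 58% |

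Reductions and permanent discontinuations barely move. Interruptions rise by 3 to 24 points over these ranges. These figures are for interruptions of any cause; a single preferred term would have smaller q and r.

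**3. Once-per-term counting.** Under the same independence, a share q × r of patients have an interruption in both periods. With r = 20% that is 0.05 × 0.20 = 1% to 0.30 × 0.20 = 6%. If both carry the same preferred term, the second is not visible.

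**4. Late end.** The documents give nothing from which to size this. Events after a drop back from 600 mg can add to all three categories.

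**5. If the optional efficacy summary is produced.** Best overall response, PFS and OS all start at first dose (SAP 6.1.2, 6.2.5 and 6.2.6).
- *Response.* The first scan is at Cycle 2 Day 1, normally at or before escalation, although the visit windows overlap. If 20% to 60% of responders (assumed) first respond there, a 50% rate (assumed) includes 0.50 × 20% = 10 to 0.50 × 60% = 30 points first seen on 450 mg.
- *Time to event.* Each time includes 28/30.4375 = 0.92 to 35/30.4375 = 1.15 months before escalation. With S(t) = 0.5^(t/m), where m is the assumed median PFS from escalation, and no progression before escalation, the 6-month rate is S(6) from escalation but S(6 − 0.92) to S(6 − 1.15) from first dose:

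| m (months) | From escalation | From first dose |
|---|---|---|
| 3 | 25.0% | 30.9% to 32.6% |
| 4 | 35.4% | 41.5% to 43.2% |
| 6 | 50.0% | 55.6% to 57.1% |
| 8 | 59.5% | 64.4% to 65.7% |

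The difference is about 5 to 8 points.

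**The case against.** **The table describes a regimen.** Protocol 4.2 speaks of therapy with escalation to 600 mg, and Protocol Table 5 keeps escalated patients in Arm A. A whole-course summary of people who started at 450 mg and went up is a legitimate description, and the SAP does not label it as experience on 600 mg. That is fair. But patients enter the table only because they escalated, and the table gives no way to tell which dose preceded an event.

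**A reader might infer that the table flatters 600 mg through immortal time.** The documents do not support that. SAP 5.2 takes percentages over the number of patients in the subgroup, and no exposure-adjusted adverse event rates are planned. Event-free 450 mg time therefore does not dilute anything. Two of the three categories do not move with the start date, and the third makes 600 mg look worse.

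**A reader might also infer that early responses are wrongly credited to 600 mg in a planned analysis.** No efficacy analysis of escalated patients is specified; SAP 5.2 only allows one. Response is not an escalation criterion. The main analysis uses confirmed response, whose second determination comes at least 4 weeks later and so normally after escalation.

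**Nor does progression in Cycle 1 force a patient into the non-escalated group.** Protocol 6.8 allows treatment to continue after progression in one compartment if the investigator sees clinical benefit, and Protocol 6.7.2 has no progression criterion.

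**Onset dates are already to be listed by patient**, so timing could be recovered by hand. That limits the harm but does not make the table readable. A window defined by onset alone would also drop an event that began at 450 mg and forced a reduction at 600 mg. That part of the objection stands and shapes the fix.

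**Conclusion.** The point holds in a limited form. The only committed 600 mg safety table has a window that fits the time at 600 mg at neither end. By the documents' own definitions, it mixes Cycle 1 interruptions at 450 mg and events after a drop back with events at 600 mg.

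The early start has essentially no effect on percentages for reductions and permanent discontinuations. It raises interruptions by 3 to 24 points if 5% to 30% of escalated patients were interrupted in Cycle 1 and 20% to 40% were interrupted at 600 mg; those rates and their independence are assumptions. The effect of the late end cannot be sized.

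The optional efficacy summary would have its own dating problem, favourable to 600 mg for PFS and OS, but only if it is produced. The summaries are descriptive and the primary test is untouched. This is a low-cost improvement to make before database lock, and it does not threaten the trial's main conclusion.

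**What to change.** **In SAP 6.6.1, for escalated patients:**
- Report treatment-emergent events with onset, worsening or action taken from the first 600 mg dose to the last 600 mg dose plus 30 days, keeping the existing cut at subsequent anticancer drug therapy. Including worsening and action keeps events that began at 450 mg but led to a dose change at 600 mg.
- Show the 450 mg period before escalation separately, and apply once-per-term counting within each period.

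**In SAP 5.2, if efficacy is summarised for this group:**
- Flag responses first documented before the first 600 mg dose.
- Measure PFS and OS from an escalation landmark at Cycle 2 Day 1 plus 7 days.

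**Cost.** A few lines of SAP text and a few extra tables. Onset dates and dosing records are already collected; tying an action to a date means matching the two. There would be no single headline 600 mg response rate. No change to dosing or trial conduct is involved.
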